7.0 Statistical Considerations

9.0 Privacy/Confidentiality Issues

10.0 Follow-up and Record Retention

1.0 Background

Airway management is a critical component of anesthesia care. Failure to provide adequate ventilation and oxygenation can lead to death or permanent neurologic disability. Tracheal intubation provides a secure airway that is mandatory for many surgical procedures. Intubation of the trachea requires some type of instrument that permits visualization of the glottic inlet during insertion of the tracheal tube through the larynx and into the trachea. For many decades, the standard laryngoscope has consisted of a handle and a folding blade. The blade may be straight or curved. The purpose of the blade is to displace the tongue and sublingual tissue into the sub-mandibular space to provide the anesthesiologist with direct line-of-sight to the laryngeal inlet. Since the blade exerts pressure and displaces tissue, there is some risk of injury to the oral cavity and pharynx. Difficulty with conventional laryngoscopy can be as high as 13 percent.¹ Advances in imaging technology promoted the design of new laryngoscopes that provide an image of the larynx with indirect line-of-sight. The essence of these devices is a CCD chip or “miniature camera” that is placed at the tip of the laryngoscope. The image is transmitted to a screen for the anesthesiologist to observe. These laryngoscopes have been termed video laryngoscopes. Video laryngoscopes reduce pressure on the soft tissue of the upper airway and provide a high-resolution, wide angle view of the upper airway and larynx. Video laryngoscopes, consequently, decrease the risk of upper airway trauma and improve the ease of tracheal intubation. The first video

laryngoscope introduced into clinical practice was the Glidescope (Verathon Medical, 2003).² Since the introduction of video laryngoscopes most anesthesia departments and critical care departments, including ours, have had a steady increase in the use of video laryngoscopes in place of conventional laryngoscopes.^{3,4,5} Many anesthesiologists now use video laryngoscopes as their standard laryngoscope. Video laryngoscopy is also included in current guidelines for difficult tracheal intubation.⁶ Other video laryngoscopes in clinical use throughout the world include the CMAC (Kart Storz Imaging), Tru-View (Truphatek), McGrath (Covidien), Pentax AWS (Pentax), and the King Vision (Ambu). Some of these devices have pediatric sized blades and some do not.

Processing, portability, and cost are important aspects of video laryngoscope selection. Some devices have patient contact components that are disposable, while other devices are reusable and require processing for sterilization or high-grade disinfection. Patient cross-contamination with potentially infectious material is an increasing concern with reusable airway devices.⁷ Cost is always a concern. Some video laryngoscopes require a separate stand and monitor, and reusable blades. The initial capital outlay for such reusable devices can be as high as \$35,000. The initial financial outlay for the King Vision is \$1500.

The King Vision video laryngoscope was introduced into clinical practice in 2011. The King Vision video laryngoscope is an FDA Device Class CCW instrument that is 510(K) exempt: regulation number 868.5540. This device

consists of a reusable, imaging wand that is inserted into a disposable blade (size 3). Published reports have documented the value of the King Vision video laryngoscope in older children and adults.^{8,9} The size 3 blade is suitable for intubation of adults and children as young as 8 years. Ambu now makes size 1 and 2 blades suitable for intubation of infants and young children. The purpose of this study is to evaluate the performance of the King Vision video laryngoscope in younger patients. Advantages of the King Vision scope include a very high success rate of first pass intubation, relatively low cost (\$11 per intubation) and extreme portability.

2.0 Rationale and Specific Aims

The purpose of this study is to evaluate the performance characteristics of the King Vision video laryngoscope in pediatric patients between the ages of one month and 10 years of age. If the performance is satisfactory, this device may become a standard laryngoscope for tracheal intubation in elective and emergent tracheal intubations.

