# Data Collection Sheet

## King Vision Video Laryngoscope aBlade System for Use in Children

Subject ID _____ Date: _____	Age: _____	ASA:    I    II    III	Patient sticker
Gender: M F	Weight: _____ kg	Height: _____ cm	PI or Sub-I: _____

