3.0 Inclusion/Exclusion Criteria

Inclusion:

1. All children between the ages of 1 month to 10 years with a normal preoperative airway examination
2. Scheduled for a surgical procedure that requires tracheal intubation shall be included.

Exclusion:

1. Patients that will be excluded are those with an airway examination or previous anesthesia history that suggests difficulty with mask ventilation.

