5.0 Study Procedures

All procedures shall be routine procedures for the administration of anesthesia appropriate for the age of the child and the type of surgical procedure. This is a data collection only study .

1. The technique of anesthesia induction will be determined for each patient by the anesthesiologist of record.
2. After the induction of anesthesia, and when the patient is at an adequate depth of anesthesia, tracheal intubation will be performed with the King Vision video laryngoscope by one of the investigators.
3. Data recorded will include gender, age, and weight of the patient.
4. Data specific to the device and tracheal intubation include; size and type of blade (standard vs. channeled), blade tip position, Cormack-Lehane score, tracheal tube size, and a subjective scoring of tracheal tube delivery.
5. See the attached data collection sheet.

6.0 Reporting of Adverse Events or Unanticipated Problems Involving Risk to Participants or Others

We do not anticipate adverse events related to this study. This is a data collections only study therefore there are minimal to no risks to the subjects.

There is a minimal risk of loss of confidentiality. PHI will be accessed for recruitment purposes by the clinical care team and/or research care team.

All data shared with the sponsor will be unidentifiable.

Any reports of adverse events can be made to:

[name]. @ Office number: [contact] or [contact]

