7.0 Statistical Considerations

As this is not a comparative study, only descriptive statistics will be applied.

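### Does the lack of an urgency field undermine the results, given that Section 2 mentions emergent as well as elective use?

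*Combined protocol and SAP*

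**What the plan says.** In the combined protocol and SAP, Section 2.0 opens with the purpose, which is to evaluate the performance characteristics of the device in children from one month to 10 years. The next sentence concerns adoption: "If the performance is satisfactory, this device may become a standard laryngoscope for tracheal intubation in elective and emergent tracheal intubations".

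Section 3.0 asks for children "with a normal preoperative airway examination" and adds "Scheduled for a surgical procedure that requires tracheal intubation shall be included". Its only exclusion is an "airway examination or previous anesthesia history that suggests difficulty with mask ventilation". Urgency is neither defined nor excluded.

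Section 5.0 lists the patient variables ("Data recorded will include gender, age, and weight of the patient") and the device variables ("Data specific to the device and tracheal intubation include; size and type of blade (standard vs. channeled), blade tip position", followed by Cormack-Lehane score, tube size and a delivery score). It then refers to the data collection sheet. The sheet's header begins "Subject ID _____ Date" and continues with age, ASA class I to III, gender, weight, height, operator and a patient sticker. The rest covers view, blade, tube, stylet, attempts, time, technique and complications.

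Section 4.0 sets enrolment at 100 with no comparison group. Section 7.0 says "As this is not a comparative study, only descriptive statistics will be applied".

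**The concern.** Section 2.0 names two settings, and the planned dataset has no variable to tell them apart. Because *scheduled* is undefined, the 100 children could be all elective or could include some urgent booked cases, and the tables would not show which. In a purely descriptive study the tables are the whole result.

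If urgent cases were present, the report could not say how many there were or give their attempts, insertion times, laryngeal views or complications, and the elective figures would be mixed with them. The risk is that an overall success rate is later read as evidence for emergent intubation when few or no such cases were observed. The apparent remedy is cheap: one tick box and an extra set of table columns.

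**Working it through.** **Text check.** The factual parts hold. Section 2.0 names both settings, Section 3.0 leaves *scheduled* undefined, and neither Section 5.0 nor the available sheet text has an urgency item. The 100 in Section 4.0 comes with no derivation, so there is no planned figure to reproduce.

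**Does a planned result need urgency?** The aim in Section 2.0 concerns performance by age range. Section 7.0 names no breakdown. The sentence on later use is conditional in both halves and sets no objective, endpoint or analysis.

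**Which patients will be enrolled?** Three items point the same way: the surgery is scheduled, a preoperative airway examination must have been normal, and the sheet lists ASA I to III with no emergency mark. Section 5.0 adds that one of the investigators intubates, which also suits planned lists. None of this strictly rules out a booked urgent case, but nothing says any are expected.

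**How much could be hidden?** Let *u* be the number of unmarked urgent cases and *F* the number of first-attempt failures among the 100. The documents give neither, so both are assumed. Success among the urgent cases is then known only to lie between

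- lower: 1 − min(F, u)/u
- upper: 1 − max(0, F − (100 − u))/u

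| | u = 5 | u = 10 | u = 20 |
|---|---|---|---|
| F = 2 | 60–100% | 80–100% | 90–100% |
| F = 5 | 0–100% | 50–100% | 75–100% |
| F = 10 | 0–100% | 0–100% | 50–100% |

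The arithmetic is right, but each lower bound places as many failures as possible in the urgent group. The same formula gives the same ranges for any unrecorded yes/no covariate, so it does not show that urgency matters here. With u = 0 it does not apply.

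**How far could the elective figure be off?** Elective success lies between 1 − min(F, 100 − u)/(100 − u) and 1 − max(0, F − u)/(100 − u). For F = 5 and u = 10, the lower value is 1 − 5/90 = 94.4% and the upper is 100%, around an overall 95%. For F = 10 and u = 10, the lower value is 1 − 10/90 = 88.9% and the upper is 100%, around an overall 90%. The overall figure can therefore overstate elective success by about one percentage point in these cases, and can understate it by at most F points.

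**What would the field buy?** Suppose urgency were recorded and every urgent intubation succeeded. The exact two-sided 95% lower limit for *n* successes in *n* is 0.025^(1/n):

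| n | Lower limit |
|---|---|
| 5 | 47.8% |
| 10 | 69.2% |
| 20 | 83.2% |
| 30 | 88.4% |
| 100 | 96.4% |

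Even with no failures, a subgroup of 5 or 10 could not support a statement about emergent use. The mark would replace a range due to missing labels with a point estimate that has wide sampling error.

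**The case for a change.** The strongest case for a change is that the point survives either reading of *scheduled*. If it means elective only, the study holds no emergent data and the Section 2.0 wording goes too far. If urgent booked cases are allowed, they are pooled without a mark. The conditional sentence is also the only statement of what the results are for, and describing who was studied is central to a descriptive report. Recovering urgency later is not assured either. The sheet carries a date and a patient sticker, but no chart review is planned, data shared with the sponsor are unidentifiable, and Section 10.0 keeps records only until the analysis and the study are complete.

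Part of this stands. The phrase about emergent use does reach beyond the population that Section 3.0 describes, and one clause would have settled what *scheduled* covers. But under the elective reading there is nothing to separate. Under the other reading, the overall tables remain a correct description of the 100 children enrolled, and the extra columns would hold counts too small to inform emergent use. Whoever reports the study can state the eligibility criterion as written, which tells readers that these were scheduled surgical patients with normal airway examinations.

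**Conclusion.** No change is needed. The missing urgency field is real, but it limits generalisability and is not a fault in any planned analysis. Every planned summary is valid for the children enrolled, with or without the field. What survives is a wording point: the prospect of emergent use in Section 2.0 is not something this sample can support, and readers should not take it as a finding.

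This rests on two judgements. The first is that *scheduled*, read with the preoperative airway examination, means planned surgery, so urgent cases are absent or few. The second is that the sentence on later use is background and not an objective. The numerical ranges rest on assumed counts and are illustrations only. The field check covers the sheet text that is available. If urgent cases were expected in number, or a claim about emergent use were to be drawn from these data, the conclusion would need to be reconsidered.

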3.0 Inclusion/Exclusion Criteria

Inclusion:

1. All children between the ages of 1 month to 10 years with a normal preoperative airway examination
2. Scheduled for a surgical procedure that requires tracheal intubation shall be included.

Exclusion:

1. Patients that will be excluded are those with an airway examination or previous anesthesia history that suggests difficulty with mask ventilation.

4.0 Enrollment/Randomization

100 patients will be enrolled. Data will be collected from the patients that the King Vision Video Laryngoscope is used. As this is not a comparative study, there shall be no randomization.

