### INTUBATION

King Vision aBlade size:    1    2    2 channeled	Standard laryngoscope blade size:    0    1    2    3
Endotracheal tube size:    2.5    3.0    3.5    4.0    4.5    5.0    5.5    6.0	Brand: _____
Blade tip position:    In vallecula    Under epiglottis	Stylet used:    Yes    No
Ease of ETT passage:    1    2    3    4    5    (1 = very easy; 2 = easy; 3 = neutral; 4 = difficult; 5 = impossible)	
Number of insertion attempts:    1    2    3    (Entry of blade into patient's mouth without the need to remove it once entered)	
Insertion time: _____ (Amount of time from Removal of facemask to the first upstroke of etCO 2 )	
Insertion Technique:  Rotated blade in from side (check all that apply)  External laryngeal manipulation  Rotate ETT counterclockwise (channeled only)  Other: _____	

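### Does the lack of a size 3 code on the King Vision blade item spoil the results when children aged 8 to 10 can be enrolled?

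*Combined protocol and SAP*

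**What the plan says.** In the combined protocol and SAP, Section 1.0 describes the original King Vision blade as size 3: "The size 3 blade is suitable for intubation of adults and children as young as 8 years". It then presents sizes 1 and 2 as newer blades for infants and young children, and gives the aim: "The purpose of this study is to evaluate the performance of the King Vision video laryngoscope in younger patients".

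Section 2.0 sets the population as "pediatric patients between the ages of one month and 10 years of age", and Section 3.0 admits "All children between the ages of 1 month to 10 years with a normal preoperative airway examination". Neither mentions blade size.

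Section 4.0 gives the sample: "100 patients will be enrolled. Data will be collected from the patients that the King Vision Video Laryngoscope is used". Section 5.0 says that "tracheal intubation will be performed with the King Vision video laryngoscope by one of the investigators". It also lists age and the size and type of blade among the data to be recorded, and refers to the attached data collection sheet.

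That sheet (the SAP document, under INTUBATION) has the item "King Vision aBlade size: 1 2 2 channeled". It offers no size 3 and no free-text option. A separate item for the standard laryngoscope blade runs from 0 to 3. Age is entered at the top of the sheet.

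Section 7.0 limits the analysis: "As this is not a comparative study, only descriptive statistics will be applied".

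**The concern.** Read together, these passages seem to leave a hole. A child of 8, 9 or 10 is eligible. The Background associates size 3 with that age and upward. Any King Vision intubation counts toward the 100. Yet the blade item has no code for size 3, so a patient could meet every enrolment condition while a required item had no valid printed answer.

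Miscoding is possible as well as a blank. The only printed blade code of 3 sits in the neighbouring item for the standard laryngoscope, and Section 5.0 uses the word standard in another sense, for a King Vision blade without a channel. A size 3 King Vision intubation circled there could later be taken for use of a conventional laryngoscope.

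At stake would be the meaning of the overall description. The Background already cites published support for the device in older children and adults; the new question is how the small blades perform. If an unknown number of size 3 intubations were pooled with them, the headline figures would describe a mixture, and a table by blade would be incomplete.

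**Working it through.** The plan gives 100 with no power, precision target or effect size, so there is no sample-size figure to reproduce. The check has two parts: whether the passages conflict, and how large the effect could be.

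**Do the passages conflict?**

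1. Section 1.0 gives a lower age from which size 3 is suitable. It does not say that children of 8 to 10 must have it, or that sizes 1 and 2 are unsuitable for them. The term young children is left undefined.
2. Section 5.0 brings in the data collection sheet, whose King Vision item lists only sizes 1, 2 and 2 channeled. The Background's purpose sentence comes shortly after sizes 1 and 2 are introduced and points to younger patients.
3. A study of sizes 1 and 2 in children up to 10 years is consistent with every passage. The missing code for size 3 is as much a sign of that intention as an oversight.
4. No passage says size 3 will be used, and none rules it out. The gap is that the protocol does not name the blades under study.

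**How many children could be affected?**

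The documents give no age distribution, so uniform ages from 1 month are assumed.

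- Up to the 10th birthday: (10 − 8)/(10 − 1/12) = 2/9.92 = 20.2%.
- Up to the 11th birthday: (11 − 8)/(11 − 1/12) = 3/10.92 = 27.5%.

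That is about 20 to 27 of 100. Even at an assumed true share of 5%, the chance of at least one such child is 1 − 0.95^100 = 99.4%. Some children of 8 or over are thus likely to be enrolled. How many of them would receive size 3 cannot be derived from the documents.

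**How far could the results move?**

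As an upper bound, suppose every child of 8 or over had size 3, leaving 80 or 73 on the coded blades. At an assumed first-attempt success of about 90%, the exact (Clopper-Pearson) 95% intervals are:

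| Patients | Successes | 95% interval | Width (points) |
|---|---|---|---|
| 100 | 90 | 82.4% to 95.1% | 12.7 |
| 80 | 72 | 81.2% to 95.6% | 14.3 |
| 73 | 66 | 81.2% to 96.1% | 14.8 |

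The loss of precision on the coded blades is at most about 2 points of interval width.

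The shift from mixing is the share on size 3 times the difference in success. With an assumed 10-point advantage for size 3 it is 0.20 × 10 = 2.0 to 0.27 × 10 = 2.7 points. With 5 points it is 0.20 × 5 = 1.0 to 0.27 × 5 = 1.35 points. With no size 3 use it is zero.

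**Could the groups still be separated?**

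Yes, by age. The worry is confined to children of 8 and over, so on its own premise a summary of those under 8 contains no size 3 intubations. Age is recorded for every patient. A blank blade item in an older child would also stand out and could be queried.

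**The case for a change.** The best argument for a change is that it is cheap and that description is all this study produces. Section 2.0 ties a practical conclusion to it: if performance is satisfactory, the device may become a standard laryngoscope. One sentence in Section 4.0 and one more option on the form would remove the doubt, and a blade not recorded at intubation may be hard to establish later. Separation by age is also imperfect: it isolates the small blades in children under 8, but does not show how sizes 1 and 2 performed in older children if some of those had size 3.

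Part of this stands. The protocol does not name the blades under study, the item has no free-text option, and tidier wording would do no harm. But the case depends on size 3 being used, which no passage states, and then on staff leaving the item blank or circling the wrong one although Section 5.0 asks for blade size. Writing the blade on the sheet is the obvious response, and nothing in the documents makes miscoding likely. Tables by blade and exact confidence intervals are general reporting preferences; they would be as useful, or as optional, if the form already listed size 3.

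**Conclusion.** The concern does not call for a change. The passages are accurately described, but they do not contradict one another. What remains is a missing detail, namely which blades are under study, and the data sheet and the stated purpose largely supply it.

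On the natural reading, sizes 1 and 2 only, the effect is nil. On the least favourable reading, the pooled success proportion would move by 2.0 to 2.7 points, well inside an interval 12.7 points wide. That figure rests on three assumptions found nowhere in the documents: uniform ages, size 3 in every child of 8 or over, and a 10-point difference in success. The plan makes no comparison and sets no blade targets, so no test, error rate or sample-size justification is affected. This conclusion takes no position on which blade suits which child.

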5.0 Study Procedures

All procedures shall be routine procedures for the administration of anesthesia appropriate for the age of the child and the type of surgical procedure. This is a data collection only study .

1. The technique of anesthesia induction will be determined for each patient by the anesthesiologist of record.
2. After the induction of anesthesia, and when the patient is at an adequate depth of anesthesia, tracheal intubation will be performed with the King Vision video laryngoscope by one of the investigators.
3. Data recorded will include gender, age, and weight of the patient.
4. Data specific to the device and tracheal intubation include; size and type of blade (standard vs. channeled), blade tip position, Cormack-Lehane score, tracheal tube size, and a subjective scoring of tracheal tube delivery.
5. See the attached data collection sheet.

6.0 Reporting of Adverse Events or Unanticipated Problems Involving Risk to Participants or Others

We do not anticipate adverse events related to this study. This is a data collections only study therefore there are minimal to no risks to the subjects.

There is a minimal risk of loss of confidentiality. PHI will be accessed for recruitment purposes by the clinical care team and/or research care team.

All data shared with the sponsor will be unidentifiable.

Any reports of adverse events can be made to:

[name]. @ Office number: [contact] or [contact]

